9 STATISTICAL METHODS

Statistics will be descriptive in nature. The sample size was chosen in order to provide a reasonable amount of data to assess the localization performance of Tc 99m tilmanocept in this population across the administered doses.

Demographics and baseline characteristics will be summarized for all subjects injected with tilmanocept using either descriptive statistics (sample size, mean, standard deviation, minimum, median, maximum) or frequency counts and percentages.

Primary and secondary endpoint will be determined as follows:

- The count and percentage of subjects that had at least one liver lesion identified by Tc99m tilmanocept that was also identified by FDG PET/CT.
- The count and percentage of subjects that had at least one liver lesion identified by FDG PET/CT that was also identified by Tc99m tilmanocept.
- The count and percentage of the number of liver lesions identified by Tc99m tilmanocept that were also identified by FDG PET/CT.
- The count and percentage of the number of liver lesions identified by FDG PET/CT that were also identified by Tc99m tilmanocept.
- Incidence of AEs reported for each cohort
- Other lesion localization (count and percentage of subjects with ≥ 1 localized lesion by tilmanocept).
- Exploratory statistics may be conducted for other localization of tilmanocept and quantitative uptake (radioisotope) in lesion(s) or lymph node(s).

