	
Visit 2, Injection and Imaging Procedures (Day 1):
 
Pre-Tc 99m Tilmanocept Injection:
 
• Before injection (Day 1)
◦ Urine pregnancy test will be performed for subjects of childbearing potential◦ Concomitant medication review◦ Vital Signs - within 15 minutes prior to injection 
Tc 99m Tilmanocept Injection: Subjects will receive their open label dose assignment in accordance with the 2 dosing groups.
 
Post-Tc 99m Tilmanocept Injection:
 
• Vital signs - within 15 minutes post-injection• 4-6 hours post-injection:
◦ Assessment of adverse events◦ SPECT/CT images will be obtained of the abdominal cavity (inclusive of entire liver). 
5±3 Days Post-injection Follow-Up Visit:
 
• Vital Signs• Physical Exam• Clinical labs and urinalysis• Concomitant medication review• Assessment of adverse events 
General: Up to 12 subjects (2 cohorts as described above) will be injected intravenously with Tc99m ($T_{1/2} = 6.02$ hr).
 
SPECT/CT Imaging
 
Imaging and Acquisition of Imaging Data: Image acquisition of patients in this study will be via SPECT/CT scanning. Subjects will be imaged by SPECT/CT at 4-6 hours post injection.
	
Planned Study Dates	Start of Recruitment: July 2017	End of Recruitment/ April 2018 End of Study/ July 2018
Planned number of study centers	1 center in the United States - University of Alabama at Birmingham	
Number of subjects	Total: Up to 12 evaluable subjects	
Primary Endpoint	
• Estimation of the concordance of Tc 99m SPECT/CT imaging localization with FDG PET/CT imaging per subject	

	
• Proportion of subjects not experiencing an adverse drug reaction (ADR) in each dose group
Secondary endpoints	
• Estimation of the concordance of Tc 99m SPECT/CT imaging localization with FDG PET/CT imaging per lesion• Estimation of the concordance of FDG PET/CT imaging localization with Tc 99m SPECT/CT imaging per lesion• Incidence of other areas of localization
Plan for statistical analysis	Due to the exploratory nature of this study all analyses described in this protocol will be descriptive in nature and used in support of designing a larger study.

LIST OF ABBREVIATIONS AND DEFINITIONS OF TERMS

ADR	adverse drug reaction
AE	adverse event

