1 BACKGROUND AND SIGNIFICANCE

1.1 The Unmet Needs: Need for earlier detection of hepatic metastases of colorectal primary tumors.

The liver is a common site of metastases for primary colorectal tumors [1] with between one third and one half of all patients diagnosed with colorectal cancer developing hepatic metastases [2]. Perhaps fortunately, in 30% to 40% of patients who develop advanced disease, the liver is the only site of metastatic disease [3]. As described in the next two sections, it is expected that 99mTc-tilmanocept will localize to hepatic metastases of colorectal tumors. If so, it should be possible to image such metastatic tumors using SPECT imaging (3D). There are currently available alternative imaging technologies, such as fluorodeoxyglucose positron emission tomography/computed tomography (FDG PET/CT), that are used to visualize hepatic tumors. There is a possibility that 99mTc-tilmanocept enabled imaging may have performance characteristics that would make it preferable to the alternatives for imaging of these tumors. If this is demonstrated to be the case, then 99mTc-tilmanocept would have utility as an imaging agent that could assist physicians to identify hepatic metastases, develop surgical plans and monitor patients for the efficacies of non-surgical therapies. This study will develop preliminary data relevant to the potential utility of 99mTc-tilmanocept as an imaging agent to identify and evaluate metastatic colorectal tumors in the liver.

[figure not shown]

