7.2.6 Evaluation of SPECT/CT Images

Tilmanocept localization in subjects with liver metastasis from a CRC will be evaluated through SPECT/CT image analysis by the onsite Nuclear Medicine physician. First, a "routine clinical" assessment of the overall technical adequacy of the scan will be made. It is anticipated that this would be done by viewing the projection data cine (allowing for an initial visual assessment of patient motion during the acquisition). This would be followed by a visual evaluation of the transverse reconstructed slices of the liver to assess whether hotspots could be attributed to expected metastases sites. The clinician reading the transverse SPECT liver slices will have access to the previously conducted PET scans and will report any concordance between uptake of tilmanocept with FDG at the metastases sites. The number of sites of concordance (between SPECT and PET) as well as the total number of diagnosed metastases sites for each subject imaged will be reported to the sponsor. Following the technical assessment, an overall assessment of the scan will be made. A de-identified copy of the Nuclear Medicine scan report will be provided by the site to the sponsor. For each subject the SPECT/CT scans and FDG PET/CT scans (in Digital Imaging Communications in Medicine [DICOM] format) will be forwarded to the sponsor.

All regions of interest (ROIs), standardized uptake values (SUVs), and quantitative analyses will be done by the sponsor.

Given that the imaging site has electronic transfer capabilities, each subject's scans will be transferred to the sponsors data server. If such an e-transfer is not possible, a standard "patient CD disc" will be generated and sent to the sponsor via ground mail.

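### The primary per-subject concordance in Section 9 is an any-match rate: one lesion seen on both scans is enough, discordant lesions never count, and the figure rises with lesion number.

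*Combined protocol and SAP*

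**What the plan says.** The Synopsis lists as a primary endpoint "Estimation of the concordance of Tc 99m SPECT/CT imaging localization with FDG PET/CT imaging per subject". It gives no rule for calling a subject concordant.

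Section 9 supplies the rule. It does not label its bullets primary or secondary, but only the first two concern per-subject concordance, so they must carry the primary endpoint. The first reads "The count and percentage of subjects that had at least one liver lesion identified by Tc99m tilmanocept that was also identified by FDG PET/CT". The second swaps the roles of the two scans and is otherwise worded alike: "The count and percentage of subjects that had at least one liver lesion identified by FDG PET/CT that was also identified by Tc99m tilmanocept".

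Agreement by lesion is secondary. The Synopsis names "Estimation of the concordance of Tc 99m SPECT/CT imaging localization with FDG PET/CT imaging per lesion" and its reverse, and Section 9 turns these into overall lesion counts and percentages, for example "The count and percentage of the number of liver lesions identified by FDG PET/CT that were also identified by Tc99m tilmanocept".

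Section 7.2.6 has the on-site reader send the sponsor "The number of sites of concordance (between SPECT and PET) as well as the total number of diagnosed metastases sites for each subject imaged". Section 9 plans no per-subject fraction from these counts.

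The sample is "Total: Up to 12 evaluable subjects", up to 6 per cohort. Inclusion criterion 3 (Section 4.1) requires confirmed liver metastases and sets no limit on their number. All analyses are descriptive.

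**The concern.** The two per-subject bullets describe the same event: at least one liver lesion visible on both scans. They share a numerator and can differ only in the denominator, which Section 9 does not state. Neither has a place for an FDG lesion that tilmanocept misses, or for a tilmanocept focus that FDG does not show. What is labelled concordance is therefore whether any match occurred, and that becomes easier to satisfy as the number of lesions grows.

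Three things are at stake.

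- **Intended use.** Section 1.1 hopes, conditionally, for an agent that "could assist physicians to identify hepatic metastases, develop surgical plans". Missed lesions bear on that use, and this figure cannot show them.
- **Dose.** Estimating the optimal dose is a secondary objective (Section 2.2). In two small, non-randomised cohorts, a measure that depends on lesion burden can differ between cohorts for that reason alone, or hide a real difference near its ceiling.
- **Planning.** The Synopsis says the results will help design a larger study. A rate near its ceiling and labelled concordance would be a poor planning input.

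**Working it through.** The plan gives no derivation for its sample size and no expected concordance, so there is no figure to reproduce. The check concerns how the defined measure behaves.

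**Inputs.** The match rule comes from Section 9 and the cohort size of up to 6 from the Synopsis. The per-lesion match probability *p*, the number of FDG lesions per subject *m*, and the within-subject correlation (ICC) are assumptions; the documents give none of them.

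**Step 1: independent lesions.** P(subject counted) = 1 − (1 − p)^m.

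| p | m = 1 | m = 3 | m = 5 | m = 10 |
|---|---|---|---|---|
| 0.1 | 10% | 27% | 41% | 65% |
| 0.3 | 30% | 66% | 83% | 97% |
| 0.5 | 50% | 87.5% | 97% | 99.9% |
| 0.8 | 80% | 99% | >99.9% | >99.9% |

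For p = 0.5 and m = 5: 1 − 0.5^5 = 1 − 0.031 = 0.969. With one lesion the measure equals p, so there is no inflation.

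**Step 2: correlated lesions.** Lesions in one liver share dose, background and biology, so independence is the extreme case. Under a beta-binomial model with s = (1 − ICC)/ICC, a = ps and b = (1 − p)s, P(no match) is the product of (b + i)/(a + b + i) over i = 0 to m − 1. For p = 0.5 and m = 5:

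- ICC 0.3: 0.50 × 0.65 × 0.731 × 0.781 × 0.816 = 0.151, so 85% of subjects count.
- ICC 0.5: (0.5 × 1.5 × 2.5 × 3.5 × 4.5)/(1 × 2 × 3 × 4 × 5) = 29.53/120 = 0.246, so 75% count.

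The chance that all 6 subjects in a full cohort count, with half of all lesions missed on average, is 0.969^6 = 83% if lesions are independent, 0.849^6 = 37% at ICC 0.3 and 0.754^6 = 18% at ICC 0.5.

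**Step 3: sensitivity to real differences (m = 5).** If p rises from 0.3 to 0.8, the expected matched fraction rises by 50 points. The any-match rate rises less:

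| ICC | p = 0.3 | p = 0.8 | Rise |
|---|---|---|---|
| 0 | 83.2% | 99.97% | 17 points |
| 0.3 | 64.2% | 97.7% | 34 points |
| 0.5 | 53.4% | 94.1% | 41 points |

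**Step 4: two worked cohorts.**

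- Six subjects have 5 FDG lesions each, 1 matched in each. Any match is 6/6 = 100%. The mean per-subject fraction is 1/5 = 20%, and the pooled per-lesion figure is 6/30 = 20%.
- One subject has 10 lesions, all matched, and five subjects have 1 lesion each, unmatched. The pooled per-lesion figure is 10/15 = 67%. The mean per-subject fraction is (1 + 0 + 0 + 0 + 0 + 0)/6 = 17%.

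The first cohort shows that the per-lesion endpoint can expose what the primary hides. The second shows why pooling does not give per-subject agreement.

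**The case against.** The strongest reply is that the plan as a whole does measure agreement. Section 9 sets per-lesion percentages in both directions directly below the per-subject bullets, so the first worked cohort would be reported as 100% of subjects and 20% of lesions side by side. The study is exploratory and descriptive, with no success threshold and nothing gated on the primary figure. An any-match measure also suits the feasibility question: the example for the 3-subject review in Section 7.2.2 is a cohort in which no liver metastasis was visualised in anyone. Finally, the size of the effect rests on assumed lesion counts and match rates.

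All of that stands, and it limits the point. A reader might infer that the trial cannot show how well the two scans agree; the per-lesion endpoints contradict that. A reader might also infer that the primary figure is bound to saturate. The documents do not support that either: they give no lesion counts, correlation weakens the effect, and it is absent with single lesions or a match rate near zero.

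What the reply does not answer is that the quantity named as primary is per-subject concordance, and no planned output gives it. The per-subject bullets ignore discordance, and the per-lesion bullets let subjects with many lesions dominate.

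**Conclusion.** The point holds for the primary per-subject figure, not for the plan as a whole. Whenever a subject has more than one lesion, the measure cannot separate partial from complete agreement; that follows from the definition alone. The degree of inflation depends on assumptions: with 5 lesions per subject and a 50% match rate it reads 97%, 85% or 75% at ICC 0, 0.3 or 0.5, where the matched fraction would average 50%. Because the study is descriptive and per-lesion results accompany the primary figure, this is a moderate definitional weakness. It is worth correcting mainly because correction costs so little.

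**What to change.** In Section 9:

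1. Define primary per-subject concordance as two fractions for each subject: matched lesions over FDG-identified liver lesions, and matched lesions over tilmanocept-identified liver lesions.
2. List the three counts for every subject and summarise both fractions by cohort (for example mean, median and range). Where a denominator is zero, report the fraction as undefined and state how many subjects this affects.
3. Keep the at-least-one-lesion percentage, stated once with its denominator and labelled 'any match', as a supportive feasibility result in line with Section 7.2.2.

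Section 7.2.6 already yields matched and total diagnosed sites per subject; the text should confirm that the total means FDG-identified liver lesions. Tilmanocept lesion counts are already needed as the denominator of the third Section 9 bullet, so they need only be recorded by subject.

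A complete/partial/none classification would not serve as the primary measure, because partial treats 1 of 10 and 9 of 10 alike. With 10 independent lesions and ignoring tilmanocept-only foci, partial would hold 1 − 0.75^10 − 0.25^10 = 94% of subjects at p = 0.25 and 1 − 0.2^10 − 0.8^10 = 89% at p = 0.8.

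The cost is wording, one short table for at most 12 subjects, and a headline figure that will usually look less favourable. No new scan, visit or subject is needed.

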2.2 Secondary Objective(s)

- Estimation of the optimal dose of Technetium Tc 99m tilmanocept
- Evaluation of other areas of localization of Technetium Tc 99m tilmanocept.

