7.2.2 Injection of Tc 99m tilmanocept

Both cohorts will be injected from a single syringe in a single IV injection.

Table 2. Dose Cohort and Route of Administration Groups

Dosing Cohorts	
Cohort 1	Cohort 2
IV Injection 50µg tilmanocept in 1.0 mL 2 mCi Tc99m	IV Injection 200µg tilmanocept in 1.0 mL 2 mCi Tc99m
Up to 6 subjects	Up to 6 subjects

Up to 12 subjects may be injected and imaged, divided into 2 cohorts of up to 6 subjects each.

Cohort 1 subjects will receive a Tc 99m tilmanocept IV injection in 1.0 mL and 2 mCi injected as a slow push into a catheter. At the completion of the injection, a 10 cc sterile normal saline flush will be administered. The preferred site of IV placement will be the left or right antecubital vein.

Cohort 2 subjects will receive a Tc 99m tilmanocept IV injection in 1.0 mL and 2 mCi injected as a slow push into a catheter. At the completion of the injection, a 10 cc sterile normal saline flush will be administered. The preferred site of IV placement will be the left or right antecubital vein.

Injection and imaging will begin with Cohort 1. After 3 subjects have been enrolled into Cohort 1, the imaging and safety data will be reviewed by the site staff and Navidea personnel to determine if additional subjects should be enrolled. If it is determined that additional enrollment will not provide meaningful data, for example no metastatic liver lesions were visualized by Tc 99m tilmanocept for any of the subjects in the cohort, enrollment into Cohort 2 will begin. After 3 subjects have been enrolled into Cohort 2, the data will be reviewed by the site staff and Navidea personnel to determine if additional subjects should be enrolled.

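### The secondary dose objective has no endpoint, and the one imaging measure that could grade the two mass doses, lesion uptake, is optional; a required descriptive uptake summary would be a cheap improvement

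*Combined protocol and SAP*

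**What the plan says.** Section 2.2 and the synopsis list as a secondary objective "Estimation of the optimal dose of Technetium Tc 99m tilmanocept". The two cohorts receive the same 2 mCi and differ in tilmanocept mass, 50 or 200 µg (Section 5.2). Neither the synopsis endpoints nor Section 9 names a measure for this objective.

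The imaging results to which Section 9 commits are counts and percentages. Per subject it has "The count and percentage of subjects that had at least one liver lesion identified by Tc99m tilmanocept that was also identified by FDG PET/CT", with the reverse direction. Per lesion it has "The count and percentage of the number of liver lesions identified by FDG PET/CT that were also identified by Tc99m tilmanocept", again with the reverse. Localization elsewhere is a count of subjects. In Section 9 only adverse-event incidence is stated to be reported by cohort.

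On continuous uptake, Section 9 says "Exploratory statistics may be conducted for other localization of tilmanocept and quantitative uptake (radioisotope) in lesion(s) or lymph node(s". Section 7.2.6 says "All regions of interest (ROIs), standardized uptake values (SUVs), and quantitative analyses will be done by the sponsor", and sends both scan sets to the sponsor in DICOM format.

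On size, Section 7.2.2 says "Up to 12 subjects may be injected and imaged, divided into 2 cohorts of up to 6 subjects each". It adds "After 3 subjects have been enrolled into Cohort 1, the imaging and safety data will be reviewed by the site staff and Navidea personnel" to decide on further enrolment, with a similar review in Cohort 2, so a cohort may stop at 3. Its example of data not worth extending is also yes/no: "for example no metastatic liver lesions were visualized by Tc 99m tilmanocept for any of the subjects in the cohort". Assignment is non-randomized (Section 5.3) and Cohort 1 goes first (Section 7.2.2). The synopsis makes all analyses descriptive and meant to support the design of a larger study.

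**The concern.** With radioactivity held constant, the imaging side of the dose question is how much lesion signal each mass gives over the surrounding liver. That is a continuous quantity. A yes/no reading records only whether it passed a visual threshold, and in a cohort of 3 to 6 a per-subject count can take only 4 to 7 values. If most subjects or most lesions are seen in both cohorts, the counts tie and say nothing about which mass gave the stronger signal. They also give the larger study no effect size or SD for uptake.

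The plan assigns the quantitative work but does not say that it will be used for the dose objective or which lesions will be measured. If regions were drawn only where a hotspot was seen, average uptake would describe only the lesions already counted as successes.

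**Working it through.** The plan has no power calculation, effect size, SD or expected detection rate, so there is no figure to reproduce. The check asks how often two cohorts tie when their true uptake differs.

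**Inputs from the protocol:** n = 6 per cohort (maximum) or 3 (possible after the review).

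**Assumptions:** log uptake is normal with equal SD in both cohorts; the cohorts differ by d = 1 SD; a lesion is identified when its uptake exceeds a fixed visual threshold; a proportion p of the lower-uptake cohort is identified. The model does not say which mass has the higher uptake.

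**Formulas, one lesion per subject**
- Detection in the higher-uptake cohort: q = Φ(Φ⁻¹(p) + d).
- P(tie) = Σₖ Bin(k; n, p) × Bin(k; n, q). P(wrong order) is the sum over pairs in which the lower-uptake cohort has the larger count.
- For cohort mean uptake: P(tie) = 0 and P(wrong order) = Φ(−d√(n/2)).

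**Worked case, n = 6, p = 0.70.** q = Φ(0.524 + 1) = 0.936. The tie terms are:
- both 6: 0.1176 × 0.6737 = 0.0793
- both 5: 0.3025 × 0.2750 = 0.0832
- both 4: 0.3241 × 0.0468 = 0.0152
- both 3 or fewer: 0.0008

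The sum is 0.178. For mean uptake, Φ(−√3) = 0.042.

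**6 vs 6, d = 1 SD, one lesion per subject**

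| p (lower cohort) | q | tie | wrong order | correct order |
|---|---|---|---|---|
| 20% | 56% | 9.5% | 4.6% | 85.9% |
| 30% | 68% | 8.7% | 4.5% | 86.8% |
| 50% | 84% | 10.4% | 4.8% | 84.8% |
| 70% | 94% | 17.8% | 5.5% | 76.6% |
| 90% | 99% | 51.9% | 3.6% | 44.5% |
| mean uptake | – | 0 | 4.2% | 95.8% |

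At 3 vs 3 the counts tie 19–36% of the time for p from 20% to 70%, and 71% at 90%. Correct order is 58–73% and 26% respectively, against 89.0% for mean uptake. Wrong order is 2–8% for counts and 11.0% for mean uptake.

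**Several lesions per subject** (simulation; d = 1 SD; 3 or 5 lesions in every subject; within-subject correlation 0.3 or 0.6)

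| result | 6 vs 6, p 50–70% | 6 vs 6, p 90% | 3 vs 3, p 90% |
|---|---|---|---|
| at least one lesion: tie | 18–86% | 87–99% | 93–100% |
| per-lesion count: tie | 1–5% | 11–25% | 29–48% |
| per-lesion count: wrong order | 1–4% | 4–6% | 4–6% |
| mean of subject medians: wrong order | 1–2.5% | 1–2.5% | 4–8% |

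Here p is detection per lesion. Equal lesion numbers are assumed. With unequal totals, exact ties in percentages become rarer except where both cohorts reach 0% or 100%.

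**The case against.** **The plan states no rule for judging dose.** A reader might infer that dose is scored only on yes/no identification. The documents do not say that; they attach no endpoint to the objective. The gap is a missing endpoint, with uptake the obvious candidate left optional. This stands, and the point is put that way.

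**Per-lesion percentages are also committed to.** They remove most ties when cohorts fill, subjects have several lesions and detection is moderate. This stands too. The documents give no lesion count per subject, so the one-lesion case is only one possibility. Ties remain frequent at high detection and in 3-subject cohorts.

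**Misordering.** A reader might infer that the yes/no cut often puts the doses in the wrong order. At 6 vs 6 with one lesion it does so 4–6% of the time, against 4.2% for mean uptake. The main loss is ties.

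**Power.** A reader might infer a large loss of power. The plan has no test and the fix adds none, so power does not measure the benefit.

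**A tie at the ceiling may be a fair answer.** If both masses show nearly every lesion, detection is the same for practical purposes. That is true for concordance, which stays as planned. It leaves open how far each mass clears the visual threshold.

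**What the sponsor will measure.** Section 7.2.6 says who does the quantitative work, not that every FDG-identified lesion will be measured. The fix therefore asks for some extra ROIs.

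**Conclusion.** The point holds as a cheap improvement, not as an error that invalidates the plan. The dose objective has no endpoint, the committed imaging results are all yes/no counts, and uptake statistics are optional although the quantitative work is assigned. Ties are most likely on the at-least-one-lesion result, in 3-subject cohorts and when detection is high. All the rates rest on an assumed 1 SD normal shift, and on assumed detection rates, lesion numbers and correlations; the documents supply none of these.

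An uptake summary would remove ties and give the larger study an effect size and SD. It would not make the dose comparison confirmatory. A 95% t interval for the difference in means has a half-width of 2.228 × √(2/6) = 1.29 SD at 6 vs 6, and 2.776 × √(2/3) = 2.27 SD at 3 vs 3. The cohorts are also sequential and non-randomized, so time and case mix are confounded with dose whichever measure is used.

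**What to change.** In Sections 7.2.6 and 9, make a descriptive uptake summary the required measure for the dose objective:

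- **Measure:** the log ratio of mean counts in each FDG-identified liver lesion, whether or not it was seen on SPECT, to mean counts in a lesion-free liver reference region on the same 4–6 hour SPECT/CT. Lesion ROIs are placed from the FDG PET/CT and CT position.
- **Reference region:** at a prespecified distance from any lesion, because Section 1.2 reports raised concentrations of CD206-expressing macrophages in normal tissue next to tumor. The documents give no distance, so the sponsor must set one before images are read.
- **Summary:** each subject's median ratio; individual values, mean and SD by cohort; and the between-cohort difference in means with its 95% interval, labelled descriptive because cohorts are sequential and non-randomized. Any subject without an FDG-identified liver lesion is listed as having no ratio.

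Keep all the yes/no concordance endpoints. Leave uptake in lymph nodes and other localization exploratory.

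The cost is wording in two sections, plus ROIs on lesions not seen on SPECT. No new scan, reader or subject is needed, since the sponsor receives both scan sets. A ratio within one scan needs no SUV calibration. The drawback is that ratios for small lesions will be pulled towards 1, and the report should say so.
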